¹ * All labs to be repeated if first dose occurs greater than 4 hours from last set of labs.

² ** If subject is diabetic, then follow institution's standard for glycemic monitoring.

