The second stage of amatoxin poisoning is characterized by generalized clinical improvement (resolution of gastrointestinal symptoms) that begins 24 to 48 hrs after ingestion, albeit masking the hepatic deterioration that is occurring at the same time. The liver function tests show a progressive elevation of transaminases and an evolving coagulopathy. Early renal damage may be reflected by elevations in the serum creatinine and blood urea nitrogen levels.

Grade 1: Patients develop gastroenteritis-like symptoms several hours (6-36) after ingestion but do not develop severe biochemical indications of hepatitis (peak transaminases <1000 without coagulopathy) or renal dysfunction.

Grade 2: In addition to GI symptoms patients manifest a moderate (1000-5000 IU/L) rise in transaminases and a moderate (peak INR <2.0) coagulopathy.

Stage III

Transition into the third stage can occur quite suddenly. Hepatic failure may be fulminant and is manifested by a severe increase in serum transaminases and profound coagulopathy. Patients may experience a swift progression from Stage I to Stage III or IV. The presence of hypoglycemia is a poor prognostic sign reflecting massive hepatic necrosis. Normalization of transaminases in the setting of a rising INR, creatinine, ammonia level plus worsening symptoms, should be considered to be a sign of fulminant hepatic necrosis and, hence an indicator of poor prognosis. Renal failure, due to hepatorenal syndrome and/or direct nephrotoxicity of amanitins, may result in severe oliguria or anuria. Fifty percent of patients with amatoxin poisoning may also have laboratory evidence of pancreatitis (2).

Grade 3: Patients develop a marked elevation of transaminases (>5000 IU/L) and significant coagulopathy (INR>2.0). Grade 3 is divided into two subgroups according to bilirubin values. In Grade 3a: hyperbilirubinemia is mild or absent, while Grade 3b: shows a steep and continuous rise in bilirubin (greater than 5 mg/dL).

Grade 4: A steep rise in transaminases is accompanied by a corresponding steep decline in clotting function (INR>3.0) and renal dysfunction.

Grade 1 and Grade 2 patients have the best chance of surviving amatoxin poisoning and need symptomatic treatment only. Grade 3, particularly Grade 3b patients, are at risk and should be

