3.2.1.1 Safety

Safety based on the evaluation of changes in baseline laboratory and clinical presentation while on study treatment. The laboratory values to be followed are transaminases and renal function tests (AST, ALT, bilirubin, PT/INR, creatinine, lactic acid).

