4.3 Inclusion and Exclusion Criteria

4.3.1 Inclusion Criteria

Subjects' eligibility should be reviewed and documented by the Investigator or a qualified designee before subjects are included in the study.

Subjects must meet all the following inclusion criteria to be eligible for enrolment into the study:

1. Signed Informed Consent(s) for Clinical Trial participation
2. History of eating foraged mushrooms
3. Gastrointestinal symptoms consistent with amatoxin poisoning (cramping abdominal pain, nausea, vomiting, and / or watery diarrhea) usually 24-48 hours after mushroom ingestion
4. Liver function tests consistent with amatoxin poisoning: AST or ALT above the institutions upper limit of normal after mushroom ingestion

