7.5 Statistical Analysis Methodology

In general, data will be summarized using descriptive statistics by treatment group. Continuous variables will be summarized using the mean, standard deviation, median, minimum value and maximum value. Categorical variables will be summarized using frequency counts and percentages. All data will be presented in patient data listings. Any data excluded from the summaries and statistical analyses will be flagged accordingly. Baseline value is defined as the last valid value prior to the treatment, i.e. in other words, Baseline value is treatment specific value. If the data is missing at Baseline, then the Baseline will be imputed with the corresponding value at screening. Detailed methodology for summary and statistical analyses of the data collected in this study will be documented in a Statistical Analysis Plan (SAP). This document may modify the plans outlined in the protocol; however, any major modifications of the primary endpoint definition and/or its analysis will also be reflected in a protocol amendment.

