7.7.4 Laboratory Data

Clinical laboratory data consists of clinical chemistry, hematology, and other parameters. These data will be summarized by treatment. For clinical laboratory tests, listings of values for each patient will be presented with abnormal or out of range values flagged. The laboratory data will be presented in System International (SI) units. Numerical laboratory results will be summarized using standard summary statistics by timepoint of collection and treatment group. Baseline shift tables will be prepared for the laboratory findings ('Normal', 'Low' and 'High'). Subject listing will be prepared for the pregnancy test results for female patients.

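### The Low/Normal/High laboratory shift table cannot register worsening in the transaminase that qualified the patient

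*Combined protocol and SAP*

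**What the plan says.** Section 3.2.1.1 defines the safety assessment: "Safety based on the evaluation of changes in baseline laboratory and clinical presentation while on study treatment". It names AST, ALT, bilirubin, PT/INR, creatinine and lactic acid as the values to follow.

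Section 7.7.4 plans three laboratory outputs: summary statistics by timepoint, per-patient listings with out-of-range values flagged, and shift tables. On the last it says: "Baseline shift tables will be prepared for the laboratory findings ('Normal', 'Low' and 'High". It does not say whether the post-baseline value is the worst, the last or each visit in turn. The safety paragraph of the synopsis adds frequencies of laboratory values within, above and below the reference range.

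Section 4.3.1 sets the entry condition on enzymes, "AST or ALT above the institutions upper limit of normal after mushroom ingestion", and makes every criterion mandatory: "Subjects must meet all the following inclusion criteria to be eligible for enrolment into the study". Section 7.5 fixes the reference point: "Baseline value is defined as the last valid value prior to the treatment".

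**The concern.** A shift table counts how many patients moved from one category to a worse one. It is the only within-patient change from baseline that Section 7.7.4 names. Here the entry criterion puts at least one transaminase in the highest of the three categories before dosing. For that enzyme, a modest further rise and a very large one fall in the same cell, and that cell reads as no shift.

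What is at stake is how informative the categorical summary is for two of the markers that the protocol names as safety parameters. The table would show falls in the qualifying enzyme and never rises. A fall is also ambiguous in this disease. Section 2.2 describes a Day 4 decrease as either improvement or burn-out, and treats normalising transaminases alongside rising INR, creatinine and ammonia and worsening symptoms as a sign of massive necrosis.

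**Working it through.** The plan gives no figure on this point to reproduce. The check is a count of table cells plus a few example values.

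**Inputs**
- Shift categories: Low, Normal, High (Section 7.7.4).
- Entry: at least one of AST and ALT above the local ULN, not necessarily both (Section 4.3.1).
- Baseline: last valid pre-treatment value (Section 7.5). It can be later than the qualifying sample, because of the footnote to Table 1: "All labs to be repeated if first dose occurs greater than 4 hours from last set of labs".
- Patients whose laboratory values indicate recovery before dosing are withdrawn before treatment (Section 4.3.4). The treated set therefore remains selected for a raised enzyme.
- The protocol's own transaminase bands: below 1,000, 1,000 to 5,000 and above 5,000 IU/L (Section 2.2).

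**Step 1: planned table, baseline High.** The row has three cells: High to High (unchanged), High to Normal and High to Low (decrease). Worsening cells: 0 of 3. Decreasing cells: 2 of 3.

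**Step 2: a four-level scale from the protocol's bands** (at or below ULN; above ULN to below 1,000; 1,000 to 5,000; above 5,000 IU/L), for the three rows with a raised baseline.

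| Baseline row | Cells upward | Cells downward |
|---|---|---|
| above ULN to <1,000 | 2 | 1 |
| 1,000 to 5,000 | 1 | 2 |
| >5,000 | 0 | 3 |
| Total | 3 | 6 |

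A ceiling remains only for patients who already exceed 5,000 IU/L at baseline.

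**Step 3: example values.** The documents give no ULN, so 40 IU/L is assumed. Every row below is classified the same way for any ULN from 30 to just under 60 IU/L, provided the lower reference limit is not above 30.

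| Baseline to later value (IU/L) | Planned table | Four-level scale |
|---|---|---|
| 60 to 900 | High to High | no change |
| 60 to 3,000 | High to High | up one level |
| 60 to 8,000 | High to High | up two levels |
| 2,000 to 8,000 | High to High | up one level |
| 2,000 to 30 | High to Normal | down two levels |

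The planned table separates only the last row from the others. By Section 2.2, that row could be recovery or burn-out.

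**Step 4: the other markers.** Only AST or ALT must be raised at entry. Section 2.2 states that bilirubin is normal on admission in 90% of cases, so most patients can show Normal to High there. INR, creatinine, lactate and the other transaminase may also start normal. For these markers the table shows that a patient worsened but not by how much.

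**The case against.** The strongest reply is that the shift table is one output among several. Section 7.5 includes the maximum in its summary statistics, so a value above 5,000 IU/L would appear in the timepoint table. The listings show every value. Sections 6.4.1.2 and 9.2.2 require clinically significant laboratory changes to be recorded as adverse events. Section 2.2 says that even a very large enzyme rise need not mean a fatal course, while PT/INR carries strong prognostic weight. Section 7.4 already tabulates transplant-free proportions by INR below 2 versus 2 or more, and below 6 versus 6 or more. In a single-arm trial of a liver poison, no enzyme table can separate drug effect from disease. Section 7.5 also leaves detailed methods to the SAP.

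Most of this stands, and it limits the point. It does not remove it. A maximum or a mean at a timepoint does not count the patients who worsened, listings do not summarise, and adverse event recording depends on investigator judgment. Deferring detail to the SAP does not change the three categories that Section 7.7.4 states.

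A reader might infer three stronger things, and the documents support none of them.
- **That laboratory reporting as a whole cannot detect deterioration.** The outputs listed above can.
- **That the laboratory summary will look one-sidedly favourable.** Upward shifts in markers that start normal remain visible.
- **That a move from Grade 1 to Grade 3 would be hidden.** Grade 3 is defined by two components: "Patients develop a marked elevation of transaminases (>5000 IU/L) and significant coagulopathy (INR>2.0". Grade 1 has no coagulopathy, so a true move of that kind should also appear as Normal to High in the INR table, if INR is tabulated there.

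**Conclusion.** The point holds as a limited weakness of the categorical safety summary. For the enzyme that qualified the patient, the shift table has 0 of 3 cells for worsening, and the synopsis range frequencies share the ceiling. Every eligible patient has at least one such enzyme at screening.

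This rests on two conditions. The qualifying enzyme must still be raised at the last pre-dose sample; Section 4.3.4 makes that likely but does not guarantee it. The statement also applies enzyme by enzyme: a patient who qualifies on one transaminase may be Normal on the other and can shift upward there, so the AST and ALT tables need not be empty of worsening. The documents do not say how many patients have one enzyme raised and how many have both.

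The primary endpoint and its analysis are not affected.

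**What to change.** In Section 7.7.4, add for AST and ALT a per-patient shift from baseline category to worst on-treatment category, and state that the worst value is used. Do the same, usefully, for bilirubin, INR, creatinine and lactate. Define the categories either as multiples of the local ULN or by the protocol's own cut-points: transaminases 1,000 and 5,000 IU/L, INR 2 and 3, bilirubin 3 and 5 mg/dL. Section 2.2 gives no cut-points for creatinine or lactate, so multiples of ULN suit those. Present the enzyme shifts beside INR and bilirubin, so that a fall is not read alone as recovery. Keep Low/Normal/High for the other analytes.

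A worst-value table is designed to show worsening and will show little recovery. Recovery is already covered by the time-to-normality analysis in Section 7.5.7 for AST, ALT, bilirubin, PT/INR and creatinine.

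The cost is a few extra table rows. The values are already scheduled, and flagging out-of-range results already needs the local reference ranges. Because Section 7.7.4 calls for SI units, the bilirubin cut-points need one stated conversion. Section 7.5 allows the SAP to modify planned methods, and this change does not touch the primary endpoint.

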8 ADMINISTRATIVE PROCEDURES

Access to Data/Source Documentation

The OSI or designated representative will permit full access to data and source documentation for the purpose of clinical monitoring, audits, IRB/IEC review and regulatory inspections.

8.1 Final Clinical Study Report and Case Report Forms (CRFs)

A written clinical study report will be provided in accordance with the International Conference on Harmonization (ICH) E-3 guidelines including Annex I (Synopsis) documenting the clinical execution of the study. This report will include a description of any protocol deviations. The final report will also include reasons for withdrawals and any necessary treatment(s). The report will also include tables presenting demographics (separate summary tables for enrolled and completed subjects), and adverse events recorded during the study. In addition, the clinical study report will include a Quality Assurance statement, documenting that the report has been reviewed for completeness, accuracy, and compliance with the protocol and applicable local and federal regulations. For final clinical reporting purposes only, adverse events deemed “definite”, “probable” or “possible” will be included in the treatment-related summaries/listings.

Case Report Forms (CRFs) containing data transcribed from subject source documents (as appropriate) and copies of other source documents will be supplied by the clinical site. The OSI must sign each subject’s CRF after completion of data entry, signifying that the data entered in the CRF is complete and accurate.

8.2 Adherence to Protocol

Except for an emergency situation, in which proper care for the protection, safety and well-being of the study subjects requires medical treatment, the study will be conducted as described in the approved protocol (and amendments, if applicable), GCP and applicable SOPs. In addition, the study will be conducted in accordance with the applicable regulatory requirements of the country where the study is being conducted as well as the country where the study will be submitted. Any deviation(s) from the protocol will be recorded and presented in the final report.

8.3 Data Handling and Record Retention

All clinical information shall be recorded, handled and stored in such a way that it can be accurately reported, interpreted and verified, while the confidentiality of records of the trial subjects remains protected.

A set of CRF is required to be completed for each subject receiving study medication. The CRF is property of the sponsor and the OSI must review all CRFs prior to submission to the sponsor.

All records pertaining to the receipt and return of study supplies (particularly study medication) and copies of final CRFs, worksheets, and other pertinent source documents must be retained in accordance with ICH-GCP and the applicable regulatory requirements of the country where the study is being conducted as well as the country where the study will be submitted.

The investigator must obtain in writing the sponsor's agreement to dispose of any records, even if the retention period has been reached.

8.4 Confidentiality

Information furnished to OSIs and IRBs/Ethics Committees will be maintained in confidence by the OSI and IRB/Ethics Committee. By signing this protocol, the OSI affirms to the Sponsor that he/she will maintain, in confidence, information furnished to the IRB/Ethics Committee relevant to this study under appropriate understanding of confidentiality with such IRB/Ethics Committee.

By signing the protocol, the OSI agrees that within local regulatory restrictions and institutional and ethical considerations, the Sponsor may consult and/or copy source documents (e.g., laboratory/X-ray reports, ECG tracings, workbooks, medical records) in order to verify CRF data.

8.5 Ethics and Regulatory Authorities

Guidelines will be followed with regards to the treatment of human subjects in the study, in accordance with the requirements of the Declaration of Helsinki and International Conference on Harmonization of Technical Requirements for Registration of Pharmaceuticals for Human Use ICH-E6-R2 in addition to the regulatory requirements of the country where the study is being conducted as well as the country where the study will be submitted.

8.5.1 Institutional Review Board/Ethics Committee

The OSI is responsible for obtaining initial and continuing review (at intervals not more than once per year) of the study by an IRB/Ethics Committee, or in accordance with applicable government regulations of the country where the study is being conducted as well as the country where the study will be submitted. Ideally study will not enroll any subjects until the IRB/Ethics Committee provides written approval of the protocol and the informed consent to the investigator. Due to the critical condition of subjects with amatoxin poisoning verbal approval confirmed via email may suffice until formal written approval can be issued by the local IRB. In addition, a copy of the IRB/Ethics Committee approval documents (email and/or formal letter) must be provided to the sponsor prior to enrolling any subjects into the study.

8.5.2 Regulatory Authority

This clinical study protocol, title as well as other relevant documentation will be submitted to the local Regulatory Authorities for review and approval prior to trial start. Upon completion, the Regulatory Authorities will be notified the study has ended. The study will only be undertaken in compliance with the local regulatory requirements.

8.6 Informed Consent

A properly executed, written informed consent in compliance with current GCP guidelines and ICH guidelines shall be obtained from each patient or their legally authorized representative (LAR or next of kin) prior to entering the study. The investigator shall provide a copy of the signed and dated informed consent to the subject, and a signed and dated copy shall be maintained in the patient's medical record.

8.7 Disclosure and Publication of Clinical Study Data

The disclosure and publication of clinical study data will be detailed in the OSI Commitment Form.

8.8 End of Trial

The end of trial is considered to be the date of last subject last visit or the date of early termination of the study whichever is the later.

9 ADVERSE EVENT REPORTING

9.1 Assessment of Safety

9.1.1 Safety Parameters

Safety will be assessed by the monitoring of adverse clinical events, vital signs, clinical laboratory evaluations, and physical examinations. All adverse events occurring during the study must be recorded according to Section 9.2.2.

Findings from screening procedures, e.g., laboratory tests or physical examinations will be recorded as medical history. Clinically significant changes following the screening procedures will be recorded as adverse events.

The study period for the purpose of adverse event collection is defined as the period from the signing of a study specific informed consent to 30 days after the last dose of study medication. All adverse events that occur after the first dose of study medication through 30 days after the last dose will be considered to be treatment emergent adverse events. Any adverse event received by the clinical site for a subject who has previously exited the study needs to be forwarded to the sponsor for evaluation if within the aforementioned window.

9.2 Adverse Event Reporting

9.2.1 Definitions

Adapted from ICH Harmonised Tripartite Guideline: Clinical Safety Data Management Definition and Standards for Expedited Reporting: E2A

Adverse Event

Any untoward medical occurrence in a subject administered a medicinal product and which does not necessarily have to have a causal relationship with this treatment. An adverse event can therefore be any unfavorable and unintended sign (e.g. an abnormal laboratory finding), symptom, or disease temporally associated with the use of a medicinal product, whether or not considered related to the medicinal product.

Serious Adverse Event

An event that is fatal, life-threatening, or leads to persistent or significant disability; one that requires or prolongs hospitalization; or one that results in a congenital anomaly, or one that is a significant medical event.

Medical events that are not fatal, life-threatening, or require hospitalization may be considered serious when, based on appropriate medical judgment, they jeopardize the subject and may require [urgent] medical or surgical intervention to prevent one of the outcomes listed in this definition. Examples of such medical events include allergic bronchospasm requiring intensive treatment in an emergency room or at home, blood dyscrasias or convulsions that do not result in inpatient hospitalization, or the development of drug dependency or drug abuse.

9.2.2 Documentation of Adverse Events

The investigator or designee must record all adverse events reported by subjects that have occurred during the adverse event collection period of the study. In addition, adverse events should be solicited from subjects through open-ended questions, and as appropriate, by examination. Subjects will be evaluated for adverse events from the time of consent through study follow up visit. The subject should also be queried for any previously unreported adverse event as part of study exit procedures. All adverse events must be followed until they have resolved or stabilized.

Where possible and appropriate, the investigator should record the most important medical event or specific diagnosis rather than individual signs and symptoms (all clearly related signs, symptoms, and abnormal diagnostic procedure results should be recorded in the source document, but should be grouped under one diagnosis on the AE page).

All adverse events (including laboratory abnormalities, if they are of clinical concern), *whether or not thought to be caused by the investigational drug*, will be recorded on the CRF. The information in the CRF will include:

- The date/time of onset of any new adverse event or the worsening of a previously observed adverse event or worsening of any previously existing disease
- The event in standard medical terminology
- The duration of the adverse event
- The relationship of the adverse event to the investigational drug(s)
- The severity of the adverse event
- Seriousness of the adverse event
- Description of action taken in treating the adverse event and/or change in investigational drug administration or dose

Clinically significant abnormal laboratory values that represent a change from baseline should be recorded diagnostically as AEs (e.g. for elevated serum glucose, the AE would be described diagnostically as "hyperglycemia"). Determination of clinical significance and seriousness is based on the investigator's medical judgment. The following are examples of laboratory abnormalities that would normally qualify as adverse events:

- The abnormality suggests a change in disease severity and/or organ toxicity

The abnormality is of a degree that requires active management; e.g. change of dose, discontinuation of the drug, more frequent follow-up assessments, further diagnostic investigation, etc.

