| | 
More than 90% of all fatal mushroom poisonings worldwide are due to amatoxin containing species that grow abundantly in Europe, South Asia, and the Indian subcontinent. Many cases have also been reported in North America (1,2,3). Initial symptoms of abdominal cramps, vomiting, and a severe cholera-like diarrhea generally do not manifest until at least six to eight hours following ingestion and can be followed by renal and hepatic failure. Outcomes range from complete recovery to fulminant organ failure and death which can sometimes be averted by liver transplant.
 
Epidemiological data on mushroom poisoning, particularly poisoning with amatoxin-containing mushrooms, are rare. The true incidence of this intoxication is unknown since national data banks maintained at poison control centers have only incomplete data of this non-reportable illness [4].
 
Uncontrolled European studies and emergency use in the USA, suggest that treatment of amatoxin poisoning with Legalon® SIL drug may prevent severe morbidity (hepatic failure) and mortality.
 
This is a Phase II Multi-Center Open-Label Clinical Trial to Assess the Prevention of Liver Transplantation and/or Death Among Subjects Treated with Intravenous Silibinin (Legalon® SIL) for Amatoxin Induced Hepatic Failure. A total of 139 subjects will be enrolled into this study.
 
Legalon® SIL is formulated as a sterile lyophilisate in rubber-stoppered vials to be dissolved for intravenous infusion, containing 528.5 mg silibinin-C-2',3-dihydrogen succinate, disodium salt which is equivalent to 350 mg of silibinin according to DNPH testing or 315 mg of silibinin according to HPLC determination. The recommended daily dose is 20 mg silibinin/kg via continuous infusion over 24 hours, following a single loading dose of 5 mg silibinin/kg on the first day of treatment.
 
Subjects will be screened for eligibility and, if confirmed to meet the study criteria, will be enrolled to receive treatment of Legalon® SIL.
 
The study is comprised of a screening period of up to 24 hours from the time a potential study participant is identified. Treatment may be administered for up to 96 hours, or longer, following consultation with PPI. The final study assessment (Follow-up Visit) is to occur at 10 (+/-2) days from the last administered treatment. During screening, treatment and follow-up, assessments for medical history (only at screening), vital signs, labs and physical examination will be completed. Concomitant medications and adverse events will be recorded on every subject from the time of consent through the completion of the Follow-up Visit. Sponsor should be notified of any SAEs reported to the site and up to 30 days after discontinuation of study medication.
 |

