7.7 Safety Analyses

The safety analyses will be based on the Safety population.

The analysis set for safety summaries is defined as all subjects who received at least one dose of study medication.

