7.7.1 Adverse events

Adverse events will be summarized and listed by Preferred Term (PT) and SOC using MedDRA vocabulary (most recent) by treatment. All AEs that occur after the first dose of study medication through 30 days after the last dose will be considered to be treatment emergent AEs. The number and percentage of subjects with at least one treatment emergent AE will be presented by treatment group and events further summarized by maximum severity and relationship to study medication. The number and percentage of patients with SAE, discontinuation of study treatment due to AE (DAE), and AEs of severe intensity will be summarized by treatment. The AEs will be summarized by outcome of the event as well. Furthermore, listings of SAEs and AEs that lead to withdrawal will be provided. Summary statistics (N, %) of AEs of special interest will be also be separately tabulated.

Descriptive statistics will be provided for the following safety data. No inferential analysis of this safety data is planned. Any ECG, BP, and pulse rate abnormalities of potential clinical concern will be described.

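### Treatment-emergent adverse event percentages run to 30 days after the last dose, but scheduled questioning stops at the follow-up visit, so later non-serious events in discharged patients count only if they happen to reach the site

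*Combined protocol and SAP*

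**What the plan says.** **Window and summary.** Section 7.7.1 sets the treatment-emergent window without regard to seriousness: "All AEs that occur after the first dose of study medication through 30 days after the last dose will be considered" treatment emergent. It then plans the summary: "The number and percentage of subjects with at least one treatment emergent AE will be presented by treatment group". Section 7.7 takes as denominator "all subjects who received at least one dose of study medication". Section 9.1.1 gives the same window and defines the collection period as "the period from the signing of a study specific informed consent to 30 days after the last dose of study medication".

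**Scheduled evaluation.** Section 9.2.2 ties active evaluation to an earlier date: "Subjects will be evaluated for adverse events from the time of consent through study follow up visit". The synopsis ends recording there as well: "adverse events will be recorded on every subject from the time of consent through the completion of the Follow-up Visit". Table 1 and section 6.4 place the visit 10±2 days after the drug is stopped, and Table 1 has no later column.

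**After the visit.** Four provisions still apply:
- Section 9.1.1: "Any adverse event received by the clinical site for a subject who has previously exited the study needs to be forwarded to the sponsor", provided it falls inside the 30-day window.
- Section 9.2.2 opens by requiring the investigator to record all events that subjects report during the collection period. It later says: "All adverse events must be followed until they have resolved or stabilized".
- Section 6.4 has patients reminded to report SAEs up to 30 days after the last dose.
- Section 9.2.5 has emergency-room events up to day 30 assessed for seriousness.

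**The concern.** A percentage of subjects with an event by day 30 is normally read as meaning that each subject was asked about events up to day 30. Here a discharged patient is asked up to about day 10. After that, a new non-serious event enters the database only if it comes to the site's attention unprompted. The numerator is then built from two kinds of ascertainment over one denominator of all dosed subjects, and the table label does not show it. Spontaneous reporting generally finds fewer non-serious events than direct questioning, so the likely direction is under-counting.

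The trial has a single arm and its safety summaries are descriptive. There is no comparator whose figures would be lowered in the same way, so the percentages are read at face value. What is at stake is the meaning of the non-serious event figures in the safety tables and nothing beyond them.

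**Working it through.** The plan gives no figure for coverage of the adverse event window, so there is none to reproduce. The check is a reading of the rules side by side and a subtraction.

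**1. Rules for a discharged patient**

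| Days after last dose | New serious event | New non-serious event |
|---|---|---|
| To the follow-up visit | Solicited (9.2.2, Table 1) | Solicited (9.2.2, Table 1) |
| Visit to day 30 | Patient reminded to report (6.4); emergency-room events assessed (9.2.5) | Recorded and forwarded if it reaches the site (9.1.1, 9.2.2); nobody scheduled to ask |
| Counted in 7.7.1 to day 30? | Yes | Yes |

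The restriction to discharged patients matters: Table 1 keeps adverse event assessment in its in-hospital columns.

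**2. Days without scheduled evaluation**

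Formula: uncovered days = 30 − day of visit, counted from the last dose.
- Visit on day 12: 30 − 12 = 18
- Visit on day 10: 30 − 10 = 20
- Visit on day 8: 30 − 8 = 22

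So 18 to 22 of 30 days are uncovered, or 18/30 = 60% to 22/30 = 73%. This is a share of days and not of events.

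The synopsis also times the visit at about 10 days after discharge. If discharge comes d days after the last dose, the uncovered time is 30 − (d + 10) = 20 − d days. The documents give no d, but any delay shortens the gap.

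**3. Does the exit query close the gap?**

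Section 9.2.2 also asks that subjects be queried about unreported events at study exit, without giving a date. Two places show that exit comes before day 30.
- Section 6.2 puts the whole study at about 20 days per subject, follow-up visit included. Section 4.1 puts screening to end of treatment at about 5 days. A query 30 days after the last dose would need about 5 + 30 = 35 days, whereas a visit at day 10 to 12 needs about 15 to 17, which fits.
- Section 9.1.1 provides for events within the window in subjects who have already left the study. That would be unnecessary if exit were at day 30.

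**4. Do the other provisions close it?**

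Following events to resolution applies to known events and does not find new ones. The reminder in 6.4 concerns SAEs. Section 9.2.5 classifies emergency-room events but schedules no contact. Section 9.1.1 depends on the site receiving the event.

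**5. Scale**

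The interim summary in section 7.6 gives 20 events in 11 of 50 patients (11/50 = 22.0%), 11 of them serious, hence 20 − 11 = 9 non-serious. It does not state the window, so these cannot be split at the follow-up visit. If all 139 subjects are dosed, each one whose only event is a late, unreported, non-serious one lowers the any-event percentage by 1/139 = 0.7 points. The documents do not say how many such subjects to expect.

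**The case against.** The strongest reply is that the plan made this choice openly. Section 9.1.1 sets collection to day 30 and says how events after exit enter: active evaluation first, then spontaneous reporting. On that view, asking for more is a preference. It is also true that serious and emergency-room events are covered to day 30, that there is no between-arm comparison to bias, that events after a short infusion may well cluster early, and that section 7.5 leaves detailed methods to an SAP, which could already settle the tabulation window.

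Much of this stands, and it is why the point is minor. What it does not answer is that section 7.7.1 puts both kinds of reporting into one percentage under a 30-day label, while the synopsis says recording ends at the visit. Leaving detail to the SAP does not resolve that, because the protocol itself states the window.

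A reader might infer that adverse event recording stops altogether at the follow-up visit. The documents do not support this: the first sentence of 9.2.2 and section 9.1.1 keep the duty to record and forward reported events until day 30. Only scheduled evaluation ends at the visit.

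**Conclusion.** The point holds at minor weight. The 30-day percentages for non-serious treatment-emergent events combine solicited reporting up to the visit with spontaneous reporting over the remaining 18 to 22 days. They may be too low, by an amount the documents do not allow to be derived. This assumes a visit at 10±2 days after the last dose, a patient discharged by then, and an exit query that coincides with the visit, as the stated duration implies.

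Three stronger conclusions might be drawn, and none is supported:
- *That 60% to 73% of late events are lost.* Days are not events, no late event rate is given, and some events will be volunteered.
- *That SAE reporting or efficacy is compromised.* SAEs have their own route to day 30, and the primary endpoint in section 7.3 is assessed at 96 hours.
- *That the synopsis confidence intervals for preferred terms and System Organ Classes are biased.* Section 7.7.1 plans no intervals, and the synopsis records events only to the visit, so their use of the 30-day window would be a guess.

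The differing follow-up timings elsewhere in the protocol are a separate wording matter. Aligning them on 10±2 days would not close the gap.

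**What to change.** In sections 7.7.1 and 9.1.1 and in the SAP, tabulate non-serious treatment-emergent events through the follow-up visit and SAEs through 30 days after the last dose. List non-serious events reported spontaneously after the visit separately. Align the synopsis sentence on recording with this.

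The cost is wording only, and the change works equally for patients already past day 30. The downside is that late non-serious events appear in a listing and not in a percentage.

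A day-30 telephone contact is an optional addition if the sponsor wants to keep a 30-day percentage. It adds one call per patient still to be enrolled and cannot help those already past day 30, for whom the tabulation change would still be needed.
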